1. SYNOPSIS

Study Title	Role of CYP2B6 polymorphisms in ketamine metabolism and clearance
Objective	To determine the effects of cytochrome P4502B6 (CYP2B6) genetic variants on ketamine metabolism and clearance
Study Design	Single-center, open label, single-session study to evaluate ketamine pharmacokinetics in subjects with known CYP2B6 genotype
Study Period	Planned enrollment duration: Approximately 3 months. Planned study duration: 1 day per subject
Number of Patients	Approximately 40 healthy volunteers identified by CYP2B6 genotyping by HRPO-approved screening
Inclusion and Exclusion Criteria	
Inclusion Criteria
 
 a) 18-50 yr old b) CYP2B6*1/*1, CYP2B6*1/*6 or CYP2B6*6/*6 genotype c) Good general health with no remarkable medical conditions d) BMI < 33 e) Provide informed consent 
Exclusion Criteria
 
 a) Known history of liver or kidney disease b) Use of prescription or non-prescription medications, herbals, foods or chemicals known to be metabolized by or affecting CYP2B6 c) Females who are pregnant or nursing d) Known history of drug or alcohol addiction (prior or present addiction or treatment for addiction) e) Direct physical access to and routine handling of addicting drugs in the regular course of duty (a routine exclusion from studies of drugs with addiction potential)
Study Medication Administration	Subjects will be studied on one occasion at Washington University in St. Louis School of Medicine for administration of study drugs and blood collection. Study drug is oral ketamine HCl solution (0.4 mg/kg)
Measurements	Plasma samples are obtained for 12 hr after ketamine for measurement of parent drug and metabolite concentrations. A 24hr urine collection is also obtained. Subjective self-assessment of ketamine effect is performed using visual or verbal analog scales. Ketamine and metabolite concentrations are determined by stereoselective LC-MS/MS.
Outcomes	Primary: Plasma norketamine/ketamine AUC ratio Secondary: Plasma ketamine enantiomers and metabolite AUC, maximum concentration, apparent oral clearance, and metabolite formation clearances. Influence of CYP2B6*6 hetero or homozygote genotype on above primary and secondary outcomes

2. STUDY PROTOCOL

2.1 Background and Significance

Ketamine is a noncompetitive NMDA receptor antagonist, originally developed in 1964 as a "dissociative" anesthetic, and FDA approved in 1970. It can be administered by intravenous, intramuscular, oral, sublingual, intranasal, and rectal routes. Ketamine has been widely used for decades in anesthesia, in part, because unlike most other intravenous anesthetics, it does not significantly depress the respiratory and circulatory systems. In addition, ketamine causes significant anti-nociceptive and anti-hyperalgesic (i.e. analgesic) effects at low doses – lower than those which cause loss sedation and loss of consciousness.

More recently, there has been marked interest in the use of ketamine for other applications. Oral ketamine has been evaluated extensively for use in chronic pain management.¹ Use in pediatric sedation, analgesia, and emergency room analgesia is also of interest.²⁻⁵ More recently, has been the discovery that ketamine may be effective in the therapy of treatment-resistant depression, and with very fast response rates.⁶⁻⁹ A review of clinicaltrials.gov reveals a plethora of recent studies on ketamine. Thus there is very active research and clinical interest in ketamine.

Ketamine is administered clinically as a racemic mixture (R- and S-ketamine). Ketamine undergoes extensive metabolism, primarily via N-demethylation to norketamine, and to several other metabolites.¹⁰⁻¹³ First-pass metabolism of oral ketamine is considerable, thus it is only about 30% bioavailable. There are stereoselective differences in ketamine enantiomers metabolism and disposition. It has recently been established that cytochrome P4502B6 (CYP2B6) is the major isoform catalyzing ketamine N-demethylation *in vitro*, at therapeutic concentrations.¹⁴⁻¹⁶ A recent clinical investigation confirmed the predominant role of CYP2B6, and lack of significant CYP3A involvement, in ketamine pharmacokinetics and metabolism.¹⁷

CYP2B6 is a highly polymorphic enzyme.¹⁸ The most common variant allele, *CYP2B6*6*, found most commonly in Africans, Africans-Americans, and some Asian populations, is associated with diminished hepatic CYP2B6 enzyme expression. Compared with wild-type *CYP2B6*1/*1*. A recent *in vitro* investigation demonstrated that CYP2B6.6 (the protein encoded by the *CYP2B6*6* allele) has diminished catalytic activity towards ketamine N-demethylation (compared with wild-type CYP2B.1, and liver microsomes from humans heterozygous or homozygous for the *CYP2B6*6* allele also had diminished catalytic activity towards ketamine N-demethylation, compared with *CYP2B6*1/*1*.¹⁶

Nonetheless, there is no formal evaluation of ketamine pharmacokinetics, metabolism or clearance in *CYP2B6*6* carriers. This investigation will formally address the role of *CYP2B6* polymorphism in ketamine disposition. The research proposed will test the hypothesis that *CYP2B6* variants (*CYP2B6*6* hetero or homozygotes) *in vivo* will have decreased ketamine metabolism and clearance.

2.2 Objective

Determine the influence of CYP2B6 genetic variation, specifically *CYP2B6*6* polymorphism, on ketamine metabolism and clearance. Other, rare genotypes may be enrolled as a secondary objective.

2.3 Patient Selection

Subjects will be recruited from the greater St. Louis community that has been identified as carriers of *CYP2B6* polymorphisms (identified by participation in Washington University HRPO approved study HRPO#201203033). Thirty evaluable, healthy male and non-pregnant female 18-50 yr volunteers, in approximately equal sex distribution, will be studied. Minorities will be actively sought and included, with minority composition to reflect that of the greater Washington University/St. Louis community.

2.3.1 Inclusion Criteria

Each subject must meet all of the following criteria:

- a) 18-50 yr old
- b) *CYP2B6*1/*1, CYP2B6*1/*6 or CYP2B6*6/*6* genotype (see table) (Note: subjects of other rare genotype but with one or more 516G>T, 785A>G, 983T>C or 1459C>T polymorphism may be enrolled at PI's discretion)
- c) Good general health with no remarkable medical conditions
- d) BMI <33
- e) Provided informed consent

Allele	Protein	cDNA Change	Amino acid change	Enzyme activity	
CYP2B6*4	CYP2B6.4	785A>G	K262R	Incr.	Lang et al. , 2001; Kirchheimer et al. , 2003
CYP2B6*5	CYP2B6.5	1459C>T	R487C		Lang et al. , 2001
CYP2B6*6	CYP2B6.6	516G>T; 785A>G	Q172H; K262R	Decr. expr	Lang et al. , 2001; Tsuchiya et al. , 2004; Hofmann et al. , 2008
CYP2B6*7	CYP2B6.7	516G>T; 785A>G; 1459C>T	Q172H; K262R; R487C		Lang et al. , 2001
CYP2B6*9	CYP2B6.9	516G>T	Q172H		Lamba et al. , 2003
CYP2B6*13	CYP2B6.13	415A>G; 516G>T; 785A>G	K139E; Q172H; K262R	Decr.?	Lang et al. , 2004
CYP2B6*16	CYP2B6.16	785A>G; 983T>C	K262R; I328T	Decr. expr.	Wang et al. , 2006
CYP2B6*18	CYP2B6.18	983T>C	I328T	Decr. expr.	Klein et al. , 2005
CYP2B6*19	CYP2B6.19	516G>T; 785A>G; 1006C>T	Q172H; K262R; R336C	Decr. expr.	Klein et al. , 2005
CYP2B6*20	CYP2B6.20	503C>T; 516G>T; 785A>G	T168I; Q172H; K262R	Decr. expr.	Klein et al. , 2005
CYP2B6*26	CYP2B6.26	499C>G; 516G>T; 785A>G	P167A; Q172H; K262R	Decr	Gatanaga et al. , 2007

2.3.2 Exclusion Criteria

Subjects will not be enrolled if any of the following criteria exist:

- a) Known history of liver or kidney disease
- b) Use of prescription or non prescription medications, herbals, foods or chemicals known to be metabolized by or affecting CYP2B6
- c) Females who are pregnant or nursing
- d) Known history of drug or alcohol addiction (prior or present addiction or treatment for addiction)
- e) Direct physical access to and routine handling of addicting drugs in the regular course of duty (this is a routine exclusion from studies of drugs with addiction potential)

2.4 Design and Procedures

2.4.1 Study Design

Single-center, open-label, single-session study. The study population will be thirty evaluable healthy male and nonpregnant female 18-50 yr volunteers. All subjects will undergo the same study procedures.

2.4.2 Minimization of Bias

Placebo control and double-blinding are not required. Plasma drug concentration is not influenced by subjects' or investigators' knowledge of study aims and hypotheses. Results will be coded by enrollment number, such that pharmacokinetic data analysis will be blinded as to subjects' genotype group.

2.4.3 Pre-Study Period

Subjects who are potential candidates for the study will be educated as to the study procedures, benefits, and potential risks. They will fill out a health self-assessment, including a structured interview to screen for history of substance abuse or addiction. Each subject who qualifies for entry into the study on the basis of inclusion/exclusion criteria, prestudy evaluations and completion of an informed consent will be assigned the next available patient number. This indicates enrollment in the study. Weight will be recorded. A urine HCG pregnancy test for women of childbearing potential will be performed on the study day prior to study drug administration. Subjects who drop out of the study prior to completing the study will be replaced by using the next available patient number.

2.4.4 Study Period

Subjects will be required to refrain from: 1) alcohol for 48 hr prior to and during study days, 2) caffeine-containing beverages the day of study drug administration, 3) no grapefruit, oranges or apples or their juices for 5d prior to the study day, 4) food/liquids after midnight the day prior to drug administration (to eliminate food influence on oral drug absorption), 6) non-study medications (including over the counter and/or herbal), for 3d prior to study visit, without prior PI approval.

Subjects will be studied at Washington University in St. Louis School of Medicine. The study day will consist of an approximately 12.5-13 hr stay for drug administration, blood sampling, and urine collection. Subjects will be given a container to take home and continue their urine collection, and return the next morning to return their 24 hr urine collection.

Subjects will have a peripheral IV catheter inserted for blood sampling. Subjects are then administered 0.4 mg/kg oral racemic ketamine with 200cc water. At various time points, up to 12 hours after drug administration, venous blood samples will be drawn. Typical sampling (5cc) will be before, and 0.25, 0.5, 0.75, 1, 1.5, 2, 3, 4, 6, 8, 10, 12 hr after ketamine (13 samples, 65 ml). Coincident with blood sampling, subjective self-assessment of drug effect is performed using visual or verbal analog scales (scored from 0 to 100) for levels of alertness/sedation (almost asleep to wide awake), energy level (no energy to full of energy), confusion (confused to clear headed), clumsiness (extremely clumsy to well-coordinated), anxiety (calm/ relaxed to extremely nervous), and nausea (no nausea to worst nausea).

Two hours after dosing is completed subjects will be free to move around and be given a standard meal. Subjects will have free access to food and water during the study session and other meals will be provided during the day. At the end of the session the IV catheter is removed and subjects go home. Transportation home will be provided if required.

2.4.5 Study Drug and Doses

ketamine HCl solution (0.4 mg/kg administered orally). This is equivalent to about 0.1-0.15 mg/kg IV.

Drugs will be obtained from commercial sources or the Barnes-Jewish Hospital investigational pharmacy.

2.5 Observations and Measurements

2.5.1 Drug and metabolite concentrations

Plasma and urine concentrations of ketamine and metabolites are determined by LC-mass spectrometry using stereoselective methods developed and currently implemented in the PI's lab.

2.5.2 Calculations

Area under the curve (AUC) of plasma ketamine concentration is determined by noncompartmental methods using nonlinear regression analysis. Clearance is dose/AUC.

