2.5.3 Primary Outcome Measure

Ketamine metabolism, measured as plasma norketamine/ketamine concentration-time AUC_{0-∞} ratio, by *CYP2B6*6* hetero or homozygote genotype.

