2.5.5 Statistical Methods

Plasma and urine ketamine and metabolite concentrations are analyzed by noncompartmental methods. Outcome measures in wild-type and *CYP2B6*6* carriers will be evaluated by ANOVA. If the hypothesis is correct, we will observe diminished ketamine metabolism and clearance in *CYP2B6*6* carriers.

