2.5.6 Sample Size

This is a pilot study. We plan to study 30 evaluable subjects, assembled by *CYP2B6* genotyping, described previously (HRPO#201203033), to compose groups of 10 wild-type (*CYP2B6*1/*1*), 10 *CYP2B6* heterozygotes (*CYP2B6*1/*6*) and 10 *CYP2B6*6* homozygotes (*CYP2B6*6/*6*).

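### Does the missing rule for extrapolating the norketamine curve beyond 12 h, with 'evaluable' left undefined, undermine the primary AUC ratio?

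*Protocol*

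**What the plan says.** Protocol 2.5.3 sets the primary outcome: "Ketamine metabolism, measured as plasma norketamine/ketamine concentration-time" AUC from zero to infinity, as a ratio, by genotype. The SAP repeats it. Protocol 2.4.4 fixes the sampling window: "At various time points, up to 12 hours after drug administration, venous blood samples will be drawn", with a typical schedule whose last four times are 6, 8, 10 and 12 h.

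On calculation, Protocol 2.5.2 states that "Area under the curve (AUC) of plasma ketamine concentration is determined by noncompartmental methods using nonlinear regression analysis", and the SAP has the same sentence. Metabolites are covered in Protocol 2.5.5 and the SAP: "Plasma and urine ketamine and metabolite concentrations are analyzed by noncompartmental methods".

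On numbers, Protocol 2.5.6 says "We plan to study 30 evaluable subjects", and sections 2.3 and 2.4.1 agree with that count. The synopsis allows approximately 40 volunteers. Section 2.4.3 says that "Subjects who drop out of the study prior to completing the study will be replaced", and section 3.2 replaces withdrawals so that the required number is reached. Section 2.4.2 has the pharmacokinetic analysis done on coded results, blind to genotype group.

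**The concern.** An AUC to infinity from 12 h of data needs a terminal slope for each analyte. Norketamine is the numerator of the primary ratio, yet the one detailed AUC sentence names ketamine only, and its reference to nonlinear regression is not explained. The documents do not say how many terminal samples to use, what counts as an acceptable fit, or what to do when no slope can be estimated.

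The word evaluable does not close the gap. It is never defined, and the replacement rules cover people who drop out or withdraw. Someone who completes the day but has a noisy norketamine tail could be kept, excluded or replaced without breaching the text. Two analysts could both follow the plan and reach different primary results from the same data. If one of them excluded subjects, a study of 10 per genotype would lose precision it can hardly spare.

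**Working it through.** **The plan's own figure.** The SAP takes a 30% difference, SD 25% and two groups, and arrives at 12 per group. It states no alpha or power; assume 5% two-sided and 80%. Then n = 2(1.960 + 0.842)² × (25/30)² = 2 × 7.85 × 0.694 = 10.9, so 11 by the normal formula. The exact t calculation gives 12 (power 80.2%). The figure reproduces and is not at issue here.

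**Inputs from the documents.** Sampling times (Protocol 2.4.4); about 30% bioavailability (2.1); a 30% effect and 25% SD (SAP); 10 wild-type against 20 carriers (2.5.6, with the two *6 groups pooled).

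**Assumed, because the documents are silent.** Norketamine half-life 3, 4 or 6 h; ketamine half-life 2.5 h; absorption rate 2/h; 80% of clearance to norketamine; sample error 5% or 10%; all samples quantifiable; analysis of the log ratio at the 5% level; trapezoid plus last concentration divided by slope. The true ratio in carriers is 0.70.

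**Benchmark without tail noise.** |ln 0.70|/0.25 = 0.357/0.25 = 1.43. The noncentrality is 1.43 × √(10 × 20/30) = 3.68 on 28 degrees of freedom, so power is 0.94.

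**Step 1: choice of slope points, all subjects kept.** Share of trials in which the 5% verdict differs:

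| Comparison | Error | 3 h | 4 h | 6 h |
|---|---|---|---|---|
| last 3 v last 5 | 5% | 0.4% | 1% | 4% |
| last 3 v last 5 | 10% | 1% | 4% | 25% |
| last 4 v last 5 | 10% | 0.4% | 1% | 7% |

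Log-linear against nonlinear exponential fitting of the tail changes the verdict in at most 3% of trials up to 6 h. A whole-curve model fit was not simulated.

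**Step 2: excluding poor tails.** Suppose a completed subject is dropped when the three-point norketamine fit has adjusted R² below 0.8. This cut-off is assumed; the documents contain no such rule. At 10% error it removes 11%, 21% and 40% of subjects at 3, 4 and 6 h, and the verdict differs from keeping everyone in 5%, 10% and 30% of trials. Dropping the same shares at random, with no reference to the tail, changes the verdict in 4%, 10% and 22%. So at 3 and 4 h nearly all of the effect is loss of subjects rather than tail fitting.

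**Step 3: replacement.** The plan is for 30 evaluable subjects, so an analyst who calls someone non-evaluable is short of target. Power at 10% error, which varies by about 0.01 to 0.02 between runs:

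| Handling | 3 h | 4 h | 6 h |
|---|---|---|---|
| 3 points, poor fits dropped, not refilled | 0.89 | 0.83 | 0.59 |
| 3 points, poor fits dropped, refilled to 10 v 20 | 0.93 | 0.93 | 0.84 |
| 4 points, everyone kept | 0.93 | 0.92 | 0.84 |

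Numbers to be studied to reach 30: 30/0.89 = 33.7 (34), 30/0.79 = 38.0 (38), 30/0.60 = 50. The first two fit within approximately 40; the third does not.

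**Step 4: validity.** With no genotype effect, keeping and dropping both reject in 4% to 6% of trials at all three half-lives. The choice affects power, not the false-positive rate.

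**Step 5: inestimable slopes.** At 10% error, the chance that at least one of 30 subjects has no negative three-point slope is 0%, 0% and 6% at 3, 4 and 6 h. With four points it is 0% throughout.

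**The case for a change.** The strongest case for a change is that the gap is plain on the page, the remedy is only wording, and pharmacokinetic conventions differ on exactly these choices. Blinding stops analysts from favouring a genotype, but it does not fix the rule or say who is evaluable.

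A separate simulation supports this. It used different assumed kinetics, a three-group ANOVA and only 180 trials per setting. Four tail rules failed to agree in 6% of trials at 4 h and 5% error, and in 39% at 6 h and 10% error. At 4 h, excluding subjects with more than 30% of norketamine AUC extrapolated changed the verdict in 9% to 24% of trials. Small groups also leave little slack: on the SAP's 30% and 25%, 10 v 10 has 71.8% power and 10 v 6 has 58.0%.

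Part of this stands. With a long half-life and a noisy assay the number of slope points matters: at 6 h and 10% error, 10 v 10 power is 0.57, 0.72 and 0.77 with three, four and five points. Refilling would also overrun the planned enrolment there. But the larger discordance figures come from comparing more rules at once, or from adding exclusion limits that the plan does not contain. None of them shows that the stated method is wrong. A rule of at least four points with a log-linear fit is one sound convention; these same figures show more power with five points.

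**Conclusion.** No change follows. This is a gap that a competent pharmacokinetic analyst fills sensibly: inspect the terminal phase, use enough late samples, and do so while results are coded by enrolment number.

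The choice of slope points, with all subjects kept, alters the verdict in 0.4% to 4% of simulated trials except in one assumed corner (6 h half-life with 10% error, about 25%). The power loss from discarding poor tails depends on an exclusion rule found in neither document, and it largely disappears once the planned 30 are made up. The type I error rate is not disturbed.

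The conclusion rests on assumed half-lives, assay error, a log-ratio analysis and a 5% threshold, since the documents give none of these. Protocol 2.5.6 also describes a pilot study, so a single pass/fail verdict carries less weight than in a confirmatory trial. A norketamine half-life of 6 h or more together with sample error near 10% would make the point more serious, but nothing in the documents indicates that this applies.

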2.5.3 Primary Outcome Measure

Ketamine metabolism, measured as plasma norketamine/ketamine concentration-time AUC_{0-∞} ratio, by *CYP2B6*6* hetero or homozygote genotype.

2.5.4 Secondary Outcome Measures

- 1) ketamine enantiomers area under the plasma concentration curve (AUC_{0-∞}), maximum plasma concentration, apparent oral clearance (and by *CYP2B6*6* hetero or homozygote genotype)
- 2) norketamine enantiomers formation clearances (and by genotype)

2.5.5 Statistical Methods

Plasma and urine ketamine and metabolite concentrations are analyzed by noncompartmental methods. Outcome measures in wild-type and *CYP2B6*6* carriers will be evaluated by ANOVA. If the hypothesis is correct, we will observe diminished ketamine metabolism and clearance in *CYP2B6*6* carriers.

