STATISTICAL ANALYSIS PLAN: CYP2B6 Polymorphisms in Ketamine

7/9/13

Primary outcome measures will be ketamine metabolism, measured as plasma norketamine/ketamine concentration-time $AUC_{0-\infty}$ ratio, by *CYP2B6*6* hetero or homozygote genotype. Secondary outcome measures will include ketamine enantiomers area under the plasma concentration curve ($AUC_{0-\infty}$), maximum plasma concentration, apparent oral clearance (and by *CYP2B6*6* hetero or homozygote genotype) and norketamine enantiomers formation clearances (and by genotype). Area under the curve (AUC) of plasma ketamine concentration is determined by noncompartmental methods using nonlinear regression analysis. Clearance is dose/AUC.

Plasma and urine ketamine and metabolite concentrations are analyzed by noncompartmental methods. Outcome measures in wild-type and *CYP2B6*6* carriers will be evaluated by ANOVA. If the hypothesis is correct, we will observe diminished ketamine metabolism and clearance in *CYP2B6*6* carriers.

Sample size calculation is based on the comparison of two groups, genetic variants versus controls. Derived from the belief that detection of a 30% difference in metabolism would be clinically significant and calculating a standard deviation of 25% it is estimated that 12 patients per group is an adequate sample size.

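### The SAP sizes two groups at 12 each, the protocol plans three genotype groups of 10, and the primary genotype comparison is not unambiguously specified

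*Protocol*

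**What the plan says.** **Sizing.** The SAP's last paragraph states: "Sample size calculation is based on the comparison of two groups, genetic variants versus controls". The effect it aims at rests on the belief that "detection of a 30% difference in metabolism would be clinically significant". On variability and the resulting group size, the same paragraph reads: "calculating a standard deviation of 25% it is estimated that 12 patients per group is an adequate sample size". It gives no alpha, sidedness or target power, and does not say on what scale the 30% and 25% are measured.

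**Planned groups.** Protocol 2.5.6 calls the study a pilot with 30 evaluable subjects, "to compose groups of 10 wild-type (*CYP2B6*1/*1*), 10 *CYP2B6* heterozygotes (*CYP2B6*1/*6*) and 10 *CYP2B6*6* homozygotes". Sections 2.3 and 2.4.1 also say thirty. The synopsis says approximately 40.

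**Test.** Protocol 2.5.5 and the SAP both say: "Outcome measures in wild-type and *CYP2B6*6* carriers will be evaluated by ANOVA".

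**Primary outcome.** Protocol 2.5.3 and the SAP define it as the norketamine/ketamine AUC ratio "by *CYP2B6*6* hetero or homozygote genotype". The hypothesis in 2.1 is that heterozygous or homozygous variants "will have decreased ketamine metabolism and clearance". The synopsis gives the primary outcome as the AUC ratio alone. After the secondary outcomes it adds the influence of "hetero or homozygote genotype on above primary and secondary outcomes".

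**The concern.** The only sample size justification in the documents describes two groups of 12. The protocol recruits three groups of 10, and no comparison within 10/10/10 has 12 on each side: one pair is 10 v 10, and pooled carriers against wild-type is 10 v 20. The SAP therefore states a group size that the design does not deliver.

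The analysis text does not close the gap. An ANOVA of wild-type and carriers could have two levels (carriers pooled) or three. The SAP's sizing sentence favours two; the outcome definition and the recruitment plan favour three. No passage chooses between them, and the tests answer different questions with different power.

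At stake is whether a reader can tell which result confirms or refutes the hypothesis, and what chance the study had of finding it. Coding results so that the pharmacokinetic analysis is blind to genotype (2.4.2) protects the derivation of the AUCs. It does not fix which comparison is headlined once genotype is known.

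**Working it through.** **Inputs from the SAP:** difference 30%, SD 25%, 12 per group. **From protocol 2.5.6:** groups of 10, 10 and 10. **Assumed, because not stated:** two-sided 5%.

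**Method.** For two groups, power comes from the noncentral t distribution with noncentrality δ = (difference/SD) / √(1/n₁ + 1/n₂). For the three-group F-test, it comes from the noncentral F with λ = n Σ(group mean − overall mean)² / SD².

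**1. The SAP's own figure, read as absolute points.** 30/25 = 1.2. For 12 v 12, δ = 1.2/√(2/12) = 2.94 with 22 df, and power is 80.2%. For 11 v 11 it is 76.3%. So 12 is the smallest size reaching 80%, and the SAP's arithmetic holds for the comparison it describes.

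**2. The same inputs with 10/10/10.**

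| Primary test | Working | Power |
|---|---|---|
| One variant group v wild-type, 10 v 10 | δ = 1.2/√0.2 = 2.68 | 71.8% (18 df); 73.5% with the three-group error term (27 df) |
| Three-group F-test, heterozygotes at half effect | λ = 10 × (15² + 0 + 15²)/625 = 7.2 | 61.6% |
| Three-group F-test, heterozygotes at full or no effect | λ = 10 × (20² + 10² + 10²)/625 = 9.6 | 74.9% |
| Wild-type v pooled carriers, 10 v 20, both at 30 | δ = 1.2/√0.15 = 3.10 | 84.9% |
| Wild-type v pooled carriers, heterozygotes 15, homozygotes 30 | mean difference 22.5; δ = 0.9/√0.15 = 2.32 | 61.2% with SD 25; about 59% once the spread between the two carrier groups enters the error term |

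The half effect in heterozygotes is illustrative; no document gives one.

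**3. The log-scale reading.** If 25% is a coefficient of variation, the log SD is √ln(1 + 0.25²) = 0.246, and a 30% reduction is −ln 0.70 = 0.357, a ratio of 1.449. Then 9 v 9 gives 82.2%, 11 v 11 gives 89.8% and 12 v 12 gives 92.4%. On this scale 12 is the smallest size reaching 90%, so the stated 12 fits this reading as well as the first. With 10/10/10:

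- one pair: 86.5%, or 87.7% with the three-group error term;
- three-group F-test: 79-90% across heterozygote effects from none to full;
- pooled carriers: 95% at full effect, and about 75% if heterozygotes have a 15% reduction.

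**4. Totals.** Three groups of 12 would be 36 evaluable, not 30. The synopsis's approximately 40 could cover 36, or 30 plus replacements and the rare genotypes allowed in 2.2 and 2.3.1. The documents do not say which.

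**The case against.** The strongest reply is that the plan does name its contrast. Protocol 2.5.5 and the SAP speak of wild-type and carriers, the SAP sizes variants against controls, and the hypothesis in 2.1 covers both carrier genotypes. On that reading the comparison is 10 v 20, with an effective size of 2/(1/10 + 1/20) = 13.3 per group. At a uniform 30-point difference that gives 85%, more than the 80.2% from 12 v 12. This stands as far as it goes, so it would be wrong to say that no comparison is indicated, or that the study is underpowered on every reading. But 2.5.3 and 2.5.6 separate the carrier genotypes, and the 85% requires heterozygotes to show the full difference. If this contrast is intended, the plan should say so and replace the 12.

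A second reply is that this is a pilot. That excuses modest power and an emphasis on estimation. It does not excuse a SAP sizing that disagrees with the protocol.

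A reader might infer that the synopsis demotes the genotype comparison to secondary. The text does not support that firmly. The synopsis is a table flattened by PDF extraction, and a line about the primary and secondary outcomes above it may have stood on its own. It needs clarifying, no more.

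A reader might also infer that the figure of 12 rules out the log scale, since 9 per group would give 80% there. That presumes an 80% target, which the SAP never states.

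**Conclusion.** The discrepancy is real and should be corrected: the SAP's two groups of 12 do not match the protocol's three groups of 10 or, on their face, the synopsis's approximately 40. The primary comparison is indicated in two different ways and not settled.

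On the absolute reading, the planned design has between about 59% and 85% power at the SAP's 30-point difference, depending on the test chosen and on the heterozygote effect. On the log reading, the corresponding range is about 75% to 95%. Both rest on an assumed two-sided 5%. Sidedness matters too: one-sided 5% would give 82.5% for 10 v 10 on the absolute scale.

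The documents do not support the stronger conclusion that the trial is too small. They show that its power cannot be stated until the test, scale, alpha and sidedness are fixed.

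**What to change.** In protocol 2.5.5 and the SAP, before genotype is unblinded:

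- State whether the primary test is wild-type against pooled carriers, a three-level genotype ANOVA, or one named pair.
- Replace the SAP's 12 per group with the power that 10/10/10 gives for that test. State alpha, sidedness, and whether the 25% is an absolute SD or a coefficient of variation analysed on the log scale.
- Reconcile the total of 30 evaluable subjects with the synopsis's approximately 40.
- State whether subjects of other rare genotypes are outside the primary test.
- In the synopsis, clarify that the genotype comparison of the AUC ratio has the rank given in 2.5.3 and the SAP.

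The cost is a few sentences in three places and one recalculated power figure. No added enrolment and no particular multiplicity method is required. The downside is that the restated power may fall below 80% for some comparisons, which is acceptable to report openly in a self-described pilot.
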